25. LOCAL NUMBER OF SUBJECTS

We will attempt to recruit 400 subjects who contribute to the ultimate analysis of this work.

26. CONFIDENTIALITY

All persons accessing patient records must adhere to the following guidelines:

- The information in a patient's record cannot be disclosed without the patient's knowledge and consent; however, there are occasions when there is a legal obligation or duty to disclose information. Requests for patient information from external sources must be directed to the Medical Records Department.
- Paper medical records must be signed out by an authorized person whenever they are removed from the department.
- All paper records must be returned to the Medical Records Department.
- Medical records must not be left unattended where unauthorized persons might read them. Access to business information, including billing information, is also granted on a need-to-know basis.
- No patient records will be left open on a computer unless actively in use.
- Patient records will be closed as soon as the necessary information has been retrieved.
- Computers with access to patient medical records will be locked unless actively attended.

All computerized data will be kept on secured computers or network servers. These data will be accessible only by approved research staff, using confidential usernames and passwords. Direct

INVESTIGATOR STUDY PLAN - REQUIRED

patient identifiers will be removed from study data files as soon as possible in the data processing steps. Statistical analyses will be performed using a limited dataset. All information linking identifiable data to analysis files will be kept separate from analysis files. All data will be used only for research purposes only; published data will not contain any individual identifiers, only aggregate-level data will be reported.

Only study personnel included in IRB applications have access to project-specific data. All persons collecting or handling data are trained in human subjects' procedures, confidentiality and privacy protection. All investigators and project staff are required to receive and complete IRB and HIPAA training.

In addition, risks to confidentiality of the data collected throughout the proposed study will be addressed as follows: Assurance and confidentiality of information will be made to all participants. Data will be handled with the same confidentiality accorded to patient's medical records. Specific procedures protecting participant confidentiality will be as follows:

- ID number, as well as full name, medical record number, and dates of service will be placed on electronic study forms or records on which data are collected and/or stored (specifically medical record abstraction forms in RedCap).
- Access to data files will be secured with a password-filing system (that logs entry) and is restricted to authorized staff only
- Necessary hard-copy records containing study data of any type will be kept in locked files. Master lists linking participant information with ID number will be numbered consecutively and prepared before data collection to ensure accurate accounting. These lists will be kept locked, in duplicate, with access only by the PI and other investigators.
- All project staff will sign an oath of confidentiality to ensure their understanding of the terms of confidentiality required. They will be trained in specific procedures to ensure confidentiality.
- Sign-out procedures for all access to data files will be strictly enforced.
- All reports and publications will preserve the subjects' anonymity.

Any breach of confidentiality will be subject to a root cause analysis and preventive measures taken as appropriate. We will report any breach of confidentiality as required.

27. PROVISIONS TO PROTECT THE PRIVACY INTERESTS OF SUBJECTS

Protection for Risks Associated with Potential Loss of Confidentiality

The organizations proposing this study have systems, oversight, experienced personnel, and an organizational culture that supports the appropriate use, access and storage of confidential information. All persons collecting or handling data will be trained in human subjects' procedures, confidentiality and privacy protection. All investigators and project staff are required to receive and complete IRB and HIPAA training.

INVESTIGATOR STUDY PLAN - REQUIRED

Data for all participants will be kept strictly confidential. All research files will be kept in locked file cabinets or a locked file room. Participants will be assigned a numerical code (Study ID) for identification in the files. Names and other identifiers will be kept in separate locked files.

Individual identifier information will be removed from study data files as soon as possible in the data processing steps. All computerized data will be kept on secured computers or networks at each site. These data will be accessible only to research staff, using confidential usernames and passwords. Analysis files of de-identified data will be created at each site and will be transferred between sites using password-protected files and secure encrypted web transfer procedures. Statistical analyses will be performed using only de-identified datasets and only de-identified data will be reported. All data will be used only for research purposes only; published data will not contain any individual identifiers.

We are requesting a HIPAA waiver for the purposes of recruitment, for which we need to access patient medical record and contact information.

We will ask study participants to sign a HIPPA authorization form.

28. COMPENSATION FOR RESEARCH-RELATED INJURY

None; there are no resources available. We do not anticipate any research-related injuries. We believe the research poses no more than minimal risk to subjects.

29. ECONOMIC BURDEN TO SUBJECTS

We anticipate no economic burden to subjects in this study.

30. CONSENT PROCESS

During the patient's scheduled surgery clinic appointment, a surgery clinic staff member will then introduce the study and ask if the patient is willing to discuss the study with a study staff member after his/her surgery clinic appointment. If a patient expresses interest, the surgery clinic staff member will notify study staff member.

For patients who agree to speak, the study staff member will find a private room and discuss enrollment and informed consent. Prior to documenting written consent, the study staff member will determine if a patient needs to undergo cognitive testing. Criteria for this determination include presence in the electronic medical record of prior consent document such as for undergoing medical procedures signed by a person other than the patient, patient report of having somebody else sign for him or herself, mention of legal guardian in electronic medical record, or study staff members belief that the patient may be cognitively impaired. If legal guardian documentation in the electronic medical record indicates that medical decision-making requires guardian to sign consent, we will omit cognitive testing and proceed to obtain consent from the guardian and assent from the patient. Otherwise, to execute cognitive testing, the study staff member will administer the MiniCog test. We are waiving written documentation of consent, as the MiniCog presents no more than minimal risk of harm to subjects and involves no procedures for which written consent is

INVESTIGATOR STUDY PLAN - REQUIRED

normally required outside of the research context. If the patient passes the MiniCog assessment, the patient will sign a consent form to participate in the study. If the patient does not pass, we will obtain informed consent from a caregiver or surrogate and will ask the patient to indicate their assent. At the time of consent, the recruiter will also ask the participant and/or caregiver to sign a HIPAA authorization form for the purposes of chart review.

In order to facilitate organization/storage of informed consent and HIPAA authorization documentation and to permit participation in the research in the case of legal guardian who is not available in person to sign hardcopy of consent document, we will permit written or electronic signature. For electronic signature when guardian is not available in person we will send a link through redcap to sign the informed consent. We will then print a hard copy of signed consent form to subject and send a secure email with signed consent and HIPAA authorization to any legal guardian signing remotely. For those patients and/or guardians who are consenting in person, we will allow for electronic or written signature, and will print a hard copy for them to keep. We will then maintain all documents in REDCap system including uploading of written consent and HIPAA forms for ease of storage and IRB audit.

Note: For those who sign consents electronically, the printed hard copy will not contain the IRB stamp.

For non-English speaking patients, we will utilize an interpretive service referred to us by UMass Memorial /University Of Massachusetts Medical School interpretive services. The interpreting service is not given any information about the patients we enroll. They are only notified of the department from which we are calling from.

We will use the telephone interpretive services or a family member who is conversant in English and the language understood by the subject to conduct the interview. We will use the short forms provided by the UMass IRB. We will have the interpreter or family member act as the witness. If the interpreter is the only witness, we will send the consent form for his/her signature and keep a copy of the version signed by the interpreter. Because the involvement of each patient does not extend beyond one interview study session, we will not reassess consent with the research participant.

For test patients who will not be randomized, we will administer a separate consent that explicitly mentions that they will not be randomized but that their data will still be useful and that the intervention will still be useful to them in terms of improving their physical condition prior to undergoing surgery.

For the consent process, we will follow SOP: Informed Consent Process for Research (HRP-802) in obtaining and documenting consent.

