4. OBJECTIVES*

Surgery is a life-saving procedure for patients with cancer and can enhance quality of life for patients with intractable abdominal or thoracic disease. Although most patients tolerate the procedure well, frail older adults have as much as a threefold increase in the risk of adverse outcomes after surgery.¹ In response to this risk, some investigators^{2,4} have studied preoperative exercise interventions (a.k.a. pre-habilitation).

So far, pre-habilitation studies^{2,4} have shown improvement in endurance but not a reduction in adverse outcomes such as medical complications, discharge to nursing home, or readmission. Potential explanations are that these studies were too small to show a difference but also they did not focus on frail older adults who could benefit most from prehabilitation. A final explanation is that they relied on clinic visits with physical therapists or kinesiologists which can add to the stress and cost of surgery for patients already burdened with appointments in the short preoperative period.

A home walking prescription self-monitored with a modern pedometer (e.g. Fitbit type wristband) provides a convenient and cost-effective method for prehabilitation. Despite the apparent advantages of a home walking program, no one has demonstrated that such a program can reduce the incidence of adverse outcomes or improve physical status assessments such as endurance, balance, gait speed, strength, and self-reported function. If our investigative group establishes that a walking prescription supported by pedometer improves these assessments, we would be in a favorable position to embark on a larger study to demonstrate a reduction in adverse clinical outcomes.

There are other data that would be helpful to collect prior to embarking on the larger study. These include the role of varying duration of the walking regimen. Given the rush to proceed with surgery in anxious patients, it would be important to know how well the intervention works over the range of times available and if there exists a threshold of duration (e.g. 1-2 weeks) below which a walking prescription would have no effect.

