5. BACKGROUND*

Frail older adults are at elevated risk for adverse postoperative outcomes. With aging, impairments underlying physical function emerge, such as muscular weakness, decreased lower extremity proprioception/balance, and visual deficits. These impairments limit walking ability which in-turn limits participation in daily life activities. A more sedentary lifestyle ensues leading to further lower extremity weakness which becomes manifest in slow gait speed.⁵ These sedentary individuals also undergo significant loss of endurance/exercise capacity as their bodies becomes less efficient at using oxygen.⁶ This is significant given the stress on the body during surgery. Frail older adults are also at risk for delayed mobilization which can lead to multiple other medical complications. Afilalo et al.¹ found that cardiac surgery patients with slow gait speed, a good single marker of frailty, had more than a threefold increase in morbidity and mortality (odds ratio= 3.05 95% CI 1.23-7.54)

In that study, the authors used gait speed < 0.83 m/s which is a relatively stringent criterion for slow speed. Using a more liberal gait speed criterion (≤ 1.0 m/s), our research group still found a 1.7 fold increased risk (hazard ratio=1.71 95% CI 0.67-4.31) of developing an adverse postoperative course for older adults.⁷

A pure walking intervention (without resistance or other exercise components) can lead to improved physical status in frail older adults but it has not been tested previously in the surgical setting. Investigators have shown that long term care residents (typically frail) can participate and benefit from regular walking.⁸ Similarly, investigators with the COPD Seat study⁹ have

INVESTIGATOR STUDY PLAN - REQUIRED

proposed looking at whether a two-week movement intervention (i.e. essentially a walking program) titrated to step count can improve balance, gait speed, and strength in patients discharged after hospitalization for COPD.

Our proposal will assess the role of a walking intervention in the surgical context assessed over multiple dimensions of physical status-endurance, balance, gait speed, strength, and self-reported function.

The gains we achieve with the walking intervention will pay dividends in terms of clinical endpoints. We hypothesize that a preoperative walking intervention will lead to improvement in physical status by the time of surgery.

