Participants may walk steps over the course of a day or in one session. The initial walking prescription will also provide instructions to the participant to increase his/her number of steps each week by 10 to 20%.

A research staff member will then orient the participant to the pedometer

Weekly calls: During the interim between the day of consultation until the day of surgery, a study staff member will make weekly calls to each patient. The calls will provide participants an opportunity to report any symptoms which could warrant stopping the walking regimen and/or seeking urgent medical attention. In addition, we will train the study staff member to troubleshoot any problems setting step count targets or other problems with the pedometer. In cases in which the pedometer fails, we will budget to have additional pedometers available to mail to the patient.

Activity log: we will ask participants to log all of their physical activities-date, activity type, number of minutes. We will submit a copy of the activity log to the irb for approval prior to recruiting randomized participants to complete it.

Control subjects: a study staff member will provide general walking advice with typical warnings about when to stop (e.g., chest pain, breathing difficulty, or fall). Control subjects will receive no other intervention. We will also ask control subjects to log their physical activities.

Preoperative assessment: On the day of preoperative testing, which will usually occur three to five weeks after the baseline measurement, a research staff member or other project staff member will collect the pedometer and record the repeat physical status assessments (6MWD and SPPB). On the day of surgery, we may also place a research grade monitor on patients so as to track their steps while in the hospital.

Hospital period assessment: By the day of discharge, we will collect the research grade monitors and repeat our physical status measurements.

INVESTIGATOR STUDY PLAN - REQUIRED

In order to test the above procedures in the randomized individuals, we will enroll up to 15 patients as test patients. All these patients will undergo screening, baseline assessment/interview, follow-up assessment on day of preoperative testing, in-hospital step tracking and Hospital period assessment.

30 day assessment: Approximately 30 days from day of surgery, at office of surgery clinic, we will repeat our physical status measurements

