17. POTENTIAL DIRECT BENEFITS TO SUBJECTS*

The walking intervention has the potential to decrease adverse post-surgical outcomes for patients involved in our study, but cannot be guaranteed.

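### The consent described for the non-randomised test patients promises the physical improvement that the trial is testing, and the analysis section does not say how these patients are handled

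*Combined protocol and SAP*

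**What the plan says.** Section 11 (Procedures Involved) creates the group and gives its purpose: "In order to test the above procedures in the randomized individuals, we will enroll up to 15 patients as test patients". It then lists what they go through: "All these patients will undergo screening, baseline assessment/interview, follow-up assessment on day of preoperative testing, in-hospital step tracking and Hospital period assessment". The 30-day and 6-month assessments are not on that list, and neither is the walking prescription.

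Section 30 (Consent Process) covers their consent: "we will administer a separate consent that explicitly mentions that they will not be randomized but that their data will still be useful". The same sentence goes on to say that "the intervention will still be useful to them in terms of improving their physical condition prior to undergoing surgery". That clause is the only indication that test patients receive the intervention.

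On whether the programme improves physical condition, Section 4 (Objectives) says that "no one has demonstrated that such a program can reduce the incidence of adverse outcomes or improve physical status assessments". Section 5 (Background) puts improvement forward as a hypothesis: "We hypothesize that a preoperative walking intervention will lead to improvement in physical status by the time of surgery". The interim-analysis paragraph of Section 13 starts from the possibility that the intervention will not improve the physical status measures, and provides for revising it in that case.

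Section 13 does not mention test patients and defines no analysis population. Aim 1 rests on each participant's own change from baseline. The interim looks repeat the Aim 1 analysis after every 10 patients recruited.

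**The concern.** The main concern is the consent. Prospective participants are to be told that a benefit will occur when establishing that benefit is the purpose of Aim 1. The wording matters more because Sections 6, 18 and 30 allow adults with cognitive impairment to be enrolled through a guardian or surrogate, and nothing exempts test patients from that route. A surrogate deciding for someone else is poorly served by an unqualified promise.

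The secondary concern is the silence in Section 13. Change from baseline can be computed without randomisation, and Section 30 says these patients' data will be useful without saying for what. Whether to include them could therefore be decided after their results are known. The interim rule makes the gap concrete, because a batch in which no measure reaches its minimal clinically important difference leads to a revision of the intervention. If the first batch held only test patients, a non-randomised and apparently all-treated group would decide whether the intervention changes for the randomised patients.

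**Working it through.** **Consent wording.** The documents give no figure to reproduce here, so the check sets the statements side by side.

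| Place | Status given to improvement in physical condition |
|---|---|
| Section 30, test-patient consent | Will occur, no qualifier |
| Section 4, Objectives | Not demonstrated by anyone |
| Section 5, Background | Hypothesis |
| Section 4, Aim 1 | Question to be assessed |
| Section 13, interim analyses | May fail; revision planned if so |

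The last four agree with one another. Section 30 is the exception. The outcome is the same throughout: physical status before surgery.

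**Do test patients receive the intervention?** The Section 11 list omits the prescription, while Section 30 speaks of the intervention as useful to them. Receipt is a reasonable inference from Section 30 but is not stated outright.

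**Do their measurements reach the Aim 1 time points?** Yes. The baseline and preoperative assessments in Section 11 include the six-minute walk and the SPPB, and test patients are listed for both. Their in-hospital step tracking and hospital-period assessment also overlap with Aim 3. Overlap beyond the hospital period is not shown.

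**Interim batches.** Inputs are up to 15 test patients (Section 11) and batches of 10 recruits (Section 13).

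- 15 / 10 = 1.5 batches.
- If they are enrolled first, batch one is 10 of 10 test patients and batch two is 5 of 10.

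This needs no assumption about effect size. It does assume that test patients are enrolled before randomisation starts, which their purpose suggests but the text does not say, and that they count as recruited patients.

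**Share of the data if they were pooled.** The target is 200 in Section 24 and 400 in Section 25, with 1:1 allocation (Section 11).

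- Added to the walking arm: 15 / (100 + 15) = 13.0%, or 15 / (200 + 15) = 7.0%.
- Added to both arms together: 15 / (200 + 15) = 7.0%, or 15 / (400 + 15) = 3.6%.
- Counted inside the target: 15 / 200 = 7.5%, or 15 / 400 = 3.75%.

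These are shares of patients only. The documents give no basis for the size or direction of any difference between test patients and randomised walkers, so no shift in the estimate is computed.

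**The case against.** The strongest reply concerns the analysis. Section 11 says the test patients are there to try out procedures, and Section 30 gives them their own consent because they are not randomised. A procedures run-in kept outside the analysis is at least as natural a reading as inclusion. A reader might infer that, as written, they enter Aim 1 and contaminate the effect estimate. The documents do not support that: Section 13 is silent, and saying that data are useful does not say they serve the effect estimate. Nor do the documents say how test patients are selected, so a bias in a particular direction cannot be asserted. The interim looks set no significance test or stopping boundary, and using early patients to adjust the intervention would fit a shakedown. This reduces the analysis limb to a missing statement.

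On consent, the form itself is not available for review, so only the protocol's description of it can be criticised. That limit stands. The description is specific about content, however, and a form written to follow it would carry the same promise.

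Section 5 also says that walking alone can improve physical status in frail older adults. It adds that this has not been tested in the surgical setting, so it does not support an unqualified promise before surgery.

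Finally, a reader might cite Section 17, where benefit is described as potential "but cannot be guaranteed". That sentence concerns adverse outcomes after surgery, not physical condition before it, so it does not directly contradict Section 30. The conflict rests on Sections 4, 5 and 13.

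**Conclusion.** The consent point holds. As Section 30 describes it, the test-patient consent presents as settled the improvement that the rest of the plan treats as unproven. It affects up to 15 people, possibly including some who consent through a surrogate. The conclusion rests on the protocol's description of the form, not on the form.

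The analysis point holds only as an omission. The plan does not say whether test patients are analysed, count towards a batch of 10, or count towards the target. If they count and come first, they could fill one and a half interim batches. Pooled into the effect data, they would be between 3.6% and 13.0% of the patients concerned, depending on the target and on whether one arm or both are pooled. The documents do not show that they will be pooled, or that pooling would move the result by any given amount.

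**What to change.** 1. In Section 30 and the corresponding form, replace the promise with a statement that the walking programme may or may not improve physical condition before surgery, and that the study is being done to find out.

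2. In Section 13, add one sentence: test patients are excluded from the Aim 1 and Aim 3 effect analyses, do not count towards the interim batches of 10 or the target sample size, and are reported separately as a procedures run-in.

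3. For Aim 2, remove test patients from both sides of the calculation. Section 13 divides total time and cost by the number enrolled. Dropping only their count would leave their time and cost in the numerator and inflate the per-patient figure.

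It would also help if Section 11 stated directly whether test patients receive the walking intervention, so that this need not be inferred from the consent section.

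The cost is a wording amendment to Section 30 and the form, plus short additions to Sections 11 and 13. The downside is up to 15 fewer patients in the pooled descriptive tables. The randomised comparison loses nothing, since these patients were never allocated at random.
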